### **8.3.2.2 Change from Baseline in log-transformed observable focal-onset seizure frequency over the 16-week Treatment Period**

The analyses of the change from Baseline in observable focal-onset seizure frequency during the entire 16-week Treatment Period will be analyzed for the FAS using the ANCOVA model on the log-transformed data, as specified for the primary efficacy analysis (Section 8.1.2).

### **8.3.2.3 The 50% responder rate over the 16-week Treatment Period**

Analysis of the 50% responder rate during the entire 16-week Treatment Period will be analyzed, for the FAS, using the same logistic regression model as specified in Section 8.1.2.3.

### **8.3.2.4 The 75% responder rate over the 16-week Treatment Period**

Analysis of the 75% responder rate during the entire 16-week Treatment Period will be analyzed, for the FAS, using the same logistic regression model as specified in Section 8.1.2.3.

### **8.3.2.5 The 90% and 100% responder rates over the 12-week Maintenance Period**

Analysis of the 90% and 100% responder rates during the 12-week Maintenance Period will be analyzed for the FAS, using an exact conditional logistic regression model where treatment group is included in the model and region and Baseline SV2A use are included as strata.

### **8.3.2.6 Percent reduction in observable focal-onset seizure frequency from Baseline, over the 16-week Treatment Period**

The same methodology described in Section 8.2.1.3 will be applied.

### **8.3.2.7 Change from Baseline in log-transformed focal-onset (Type I) seizure frequency over the 12-week Maintenance Period**

The same ANCOVA model described in Section 8.1.2.1 will be applied.

### **8.3.2.8 The 50% responder rate status for focal-onset (Type I) seizures over the 12-week Maintenance Period**

Analysis of the 50% responder rate for Type I focal-onset seizures during the 12-week Maintenance Period will be analyzed for the FAS, using the same logistic regression model as specified in Section 8.1.2.3).

### **8.3.2.9 The 75% responder rate for focal onset (Type I) seizures over the 12-week Maintenance Period**

Analysis of the 75% responder rate for Type I focal-onset seizures during the 12-week Maintenance Period will be analyzed for the FAS, using the same logistic regression model as specified in Section 8.1.2.3.

### **8.3.2.10 The 90% and 100% responder rates for focal-onset (Type I) seizures over the 12-week Maintenance Period**

Analysis of the 90% and 100% responder rates for Type I focal-onset seizures during the 12-week Maintenance Period will be analyzed for the FAS, using an exact conditional logistic regression model where treatment group is included in the model and region and Baseline SV2A use are included as strata.

### **8.3.2.11 Percent reduction in focal-onset (Type I) seizure frequency from Baseline, over the 12-week Maintenance Period and the 16-week Treatment Period**

The same methodology described in Section 8.2.2.3 will be applied.

### **8.3.2.12 Change from Baseline in log-transformed Type IA1, IB, or IC seizure frequency over the 12-week Maintenance Period**

The change from Baseline in Type IA1, IB, or IC seizure frequency during the 12-week Maintenance Period by each seizure type separately will be analyzed for the FAS using the ANCOVA model on the log-transformed data, as specified for the primary efficacy analysis (Section 8.1.2).

### **8.3.2.13 The 50% responder rate for Type IA1, IB, or IC seizure over the 12-week Maintenance Period**

50% responder rate in Type IA1, IB, or IC seizure over the 12-week Maintenance Period by each seizure type separately will be analyzed for the FAS, using the same logistic regression model as specified in Section 8.1.2.3.

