6. Subjects having on average ≥ 4 spontaneous and observable focal-onset seizures per 28 days (based on Investigator assessment of subject report) with at least 1 seizure during each 4-week interval of the 8-week retrospective Baseline Period prior to entry. Additionally, subjects must experience ≥ 4 spontaneous and observable focal-onset seizures per 28 days (based on Investigator assessment of subject report) during the 4-week Baseline Period.
7. Subject has failed to achieve seizure control with ≥ 4 tolerated and appropriately chosen prior AEDs, including past and ongoing treatment, that were individually optimized for adequate dose and duration. Prior discontinued AED treatment would need to be assessed by the Investigator considering the patient medical records and patient and/or caregiver interview. "Prior AED" is defined as all past and ongoing AED treatments with a start date before the Screening Visit (Visit 1).

Concomitant epilepsy treatment

8. Subject is currently treated with an individually optimized and stable dose of at least 1 and up to 3 AEDs for the 8 weeks prior to the Screening Visit (Visit 1) with or without additional concurrent vagus nerve stimulation (VNS) or other neurostimulation treatments. The latter will not be counted as AEDs for the purpose of eligibility.

Laboratory parameter

9. Subject has clinical laboratory test results within the reference ranges of the laboratory or isolated test results that are outside the specified ranges and that are deemed as not clinically significant by the Investigator.

Birth control

10. Female subjects of child bearing potential must have a negative serum pregnancy test at the Screening Visit (Visit 1), which is confirmed to be negative by urine testing prior to the first dose of IMP at Day 1 (Visit 2) and prior to further dispensing at each study visit thereafter. Subjects will be withdrawn from the study as soon as pregnancy is known.

Female subjects will use an efficient form of contraception for the duration of the study for a period of 3 months after their last intake of IMP. Hormonal contraception may be susceptible to an interaction with the IMP, which may reduce the efficacy of the contraception method. The potential for reduced efficacy of any hormonal contraception method requires that a barrier method (preferably male condom) also be used.

Birth control methods considered as an efficient form of contraception:

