## 4.2 Handling of dropouts or missing data

### 4.2.1 Handling of missing data in seizure frequency

Unless noted otherwise, the imputation described below will be applied to seizure frequency. The responder status will be determined based on the imputed seizure frequency data. Sensitivity analyses for missing data are described in Section 8.1.2 for the primary efficacy variable.

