#### **6.3.3.7 Seizure types experienced during the Baseline Period**

The number and percentage of subjects experiencing each seizure type during the Baseline Period will be summarized based on data from Seizure Count CRF.

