#### 8.1.1.3 Percent reduction in seizure frequency from Baseline

The percent reduction in seizure frequency (PRD) from the Baseline is defined as:  $PRD = [(SFB - SFT) / SFB] \times 100$ , where SFT corresponds to the 28-day adjusted seizure frequency during an analysis period and SFB corresponds to the Baseline seizure frequency. A negative PRD indicates an increase in seizure frequency from Baseline.

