#### 8.1.1.4 75% Responder

Responder status (yes or no) for a subject is determined by the percent reduction in seizure frequency (PRD) from Baseline. A subject is defined as a 75% responder if s/he has a reduction in seizure frequency (PRD) of at least 75% from the Baseline. The 75% responder rate (RR) will be calculated as the proportion of 75% responders. For the primary efficacy variable for the

EMA, 75% responder status is calculated based on the percent reduction (PRD) from the Baseline in observable focal-onset seizure frequency during the 12-week Maintenance Period.

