#### **8.2.1.3 Percent reduction from Baseline in observable focal-onset seizure frequency over the 12-week Maintenance Period**

The third secondary efficacy variable is percent reduction from Baseline in observable focal-onset seizure frequency, over the 12-week Maintenance Period. The calculation of percent reduction from Baseline in seizure frequency is described in Section 8.1.1.2. The percent reduction in seizure frequency will be summarized descriptively.

Statistical comparisons between each PSL dose group and placebo will be performed on the FAS using the Wilcoxon-Mann-Whitney test. No multiplicity adjustment will be applied and tests will be carried out at a nominal two-sided 0.05 significance level. The Hodges-Lehmann nonparametric estimator will be used to estimate the median difference between each PSL dose group versus placebo, along with the corresponding 95% CI of the estimate.

In addition, the number and percentage of subjects within each of the following categories of percent reduction from Baseline will be summarized: <-25%, -25% to <25%, 25% to <50%, 50% to <75%, 75% to <100%, and 100%.

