### **8.3.1 Derivations of other efficacy variables**

For other efficacy variables based on seizure frequencies (observable focal-onset (Types IA1, IB, IC) and all Type I focal-onset seizures the frequencies), log-transformations, changes from Baseline, percent reduction from Baseline and Responder Rates during the evaluation period of interest are calculated similarly as described in Section 8.1.1, using the appropriate analysis period and responder criterion.

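### Do the seizure-type-specific responder and percent-reduction analyses need a rule for subjects with none of that type at Baseline?

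*SAP*

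**What the plan says.** SAP 8.3.2.12 to 8.3.2.15 break the observable focal-onset composite into its three types. For the 50% responder rate, 8.3.2.13 says the outcome "by each seizure type separately will be analyzed for the FAS, using the same logistic regression model as specified in Section 8.1.2.3". Section 8.3.2.14 is headed as the 75% rate and names the same model. Section 8.3.2.15 sends percent reduction to 8.2.2.3 and so to 8.2.1.3, where "Statistical comparisons between each PSL dose group and placebo will be performed on the FAS using the Wilcoxon-Mann-Whitney test".

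The derivations come from 8.1.1 by way of 8.3.1, under which "percent reduction from Baseline and Responder Rates during the evaluation period of interest are calculated similarly as described in Section 8.1.1". Section 8.1.1.3 defines percent reduction as PRD = [(SFB − SFT)/SFB] × 100, where "SFT corresponds to the 28-day adjusted seizure frequency during an analysis period and SFB corresponds to the Baseline seizure frequency". Section 8.1.1.4 adds: "Responder status (yes or no) for a subject is determined by the percent reduction in seizure frequency (PRD) from Baseline".

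On Baseline counts, Protocol 6.1 (criterion 6) requires at least four "spontaneous and observable focal-onset seizures per 28 days (based on Investigator assessment of subject report) during the 4-week Baseline Period". That minimum applies to IA1, IB and IC taken together. SAP 6.3.3.7 shows that individual types are expected to vary between subjects: "The number and percentage of subjects experiencing each seizure type during the Baseline Period will be summarized based on data from Seizure Count CRF".

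On missing data, SAP 4.2.1 says: "The responder status will be determined based on the imputed seizure frequency data". The rules beneath it deal with missing diary days, unknown counts and discontinuation. A known count of zero is none of these.

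**The concern.** A subject can qualify with four IB seizures and no IC seizure at Baseline. That subject is in the FAS, yet for Type IC the denominator SFB is zero. PRD is then 0/0 if the type stays absent, or a negative number over zero if it appears on treatment. Neither has a value, and nothing in SAP 3.3.1, 3.5.4, 4.2.1, 8.1.1 or 8.3.1 covers the case.

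The reference to the FAS invites a second reading: every FAS subject should be counted, and one without a qualifying reduction is a non-responder. The two readings give different denominators and different displayed rates. If many subjects lack a type, the tables would depend on a programming choice that the plan does not record.

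Section 8.3.2.14 adds to the unease. Its text says 50% under a heading that says 75%, so read literally it repeats 8.3.2.13 and leaves the 75% analysis without a description.

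**Working it through.** The plan states no figure for these analyses, so there is none to reproduce. The check has three parts.

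**1. What the formulas give.**

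- Baseline 4, treatment 1: PRD = (4 − 1)/4 × 100 = 75%, a 75% responder.
- Baseline 0, treatment 0: PRD = 0/0, undefined.
- Baseline 0, treatment 3: PRD = −3/0, undefined.

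Responder status is a function of PRD (8.1.1.4). With PRD undefined there is no status to enter in the logistic regression and no value to rank in the Wilcoxon-Mann-Whitney test. FAS membership does not supply an outcome that the derivation cannot produce. Read straight through, the text leads to exclusion of zero-Baseline subjects for that type. Having the type at Baseline is settled before randomisation, so the restricted comparison remains randomised.

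**2. How much the alternative coding would move the result.** Inputs: the planned 75% responder rates for the composite in SAP 2.7, 0.121 for placebo and 0.342 for 400mg bid, borrowed here for a single type; 80 per arm; and a share q of FAS subjects with the type at Baseline. The documents do not give q, so it is varied.

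- Excluded, any q: difference = 0.342 − 0.121 = 0.221; odds ratio = (0.342/0.658)/(0.121/0.879) = 3.78.
- Coded non-responder: each rate is multiplied by q. At q = 0.5 the rates are 0.0605 and 0.171, the difference is 0.1105, and the odds ratio = (0.171/0.829)/(0.0605/0.9395) = 3.20.

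| q | n per arm if excluded | Difference, excluded | Difference, non-responder | OR, excluded | OR, non-responder |
|---|---|---|---|---|---|
| 0.8 | 64 | 22.1 points | 17.7 points | 3.78 | 3.51 |
| 0.5 | 40 | 22.1 points | 11.05 points | 3.78 | 3.20 |
| 0.3 | 24 | 22.1 points | 6.6 points | 3.78 | 3.04 |

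The raw difference scales with q. The odds ratio, which is what the 8.1.2.3 model estimates, falls by (3.78 − 3.20)/3.78 = 15% at q = 0.5. These odds ratios are unadjusted, whereas the model includes log-transformed Baseline frequency. If that covariate is type-specific, all zero-Baseline subjects sit at ln(0 + 1) = 0 and it absorbs most of them. In a simulation with response independent of the Baseline count among those who have the type, the adjusted odds ratio stayed close to 3.8 at all three values of q.

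Power does not favour non-responder coding. By the pooled normal approximation at q = 0.5 and two-sided 0.05, exclusion gives 65% with 40 per arm, against 59% with 80 per arm under non-responder coding.

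**3. What depends on it.** Section 8.3.2 places these tests at a nominal 0.05 without multiplicity adjustment. The type-specific variables are not in Protocol 4.1.3, SAP 2.3.3 or Table 8-1. For the composite and for all Type I seizures, an eligible subject has a Baseline count of at least four, so SFB cannot be zero. The change in log frequency by type (8.3.2.12) uses ln(x + 1), which is defined at zero.

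**The 8.3.2.14 text.** The section heading and the table of contents both say 75%, and 8.3.2.13 already covers 50%. Only one reading makes sense of all three.

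**The case for a change.** The best argument for a change is that the SAP does write this kind of rule elsewhere. Percentage of school or work days lost (8.3.2.25) is confined to subjects with a positive number of such days, and seizure freedom (8.3.2.16) has its own Completer Set. Silence here could therefore be filled badly.

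The worst case is a mixture: subjects with 0/0 drop out, while those with a new occurrence are counted as non-responders or placed in the lowest category of 8.2.1.3. Inclusion would then turn on what happened after randomisation, and the comparison would no longer be clean. The Addendum repeats every table for Japan and non-Japan, so a poor choice would carry through.

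It stands that no sentence forbids the mixture. Nothing points to it either: PRD is equally undefined in both situations, and the text gives no ground for separating them. Coding zero-Baseline subjects as responders has no textual support at all, since it would credit a subject who developed new seizures on treatment.

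A request for n per arm is largely met already. Under 6.3.3, the summary in 6.3.3.7 is produced by treatment group on the FAS, so a reader can see how many subjects in each arm had each type at Baseline.

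**Conclusion.** The SAP omits a sentence, but the omission calls for no change to the plan. The definitions in 8.1.1.3 and 8.1.1.4 leave a zero-Baseline subject without a responder status, which leads an analyst to the sensible restriction. The only other reading with any support, non-responder coding, is also a valid randomised comparison, answering a slightly different question about the whole FAS.

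The gap between the two readings depends on an unknown q. At q = 0.5, with the planned composite rates borrowed for one type, it is 22.1 against 11.05 points, or an unadjusted odds ratio of 3.78 against 3.20. It shrinks as q approaches 1 and largely disappears from the modelled odds ratio if the Baseline covariate is type-specific.

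No confirmatory claim rests on these nominal analyses. The primary, secondary and all-Type-I results and the ANCOVA in 8.3.2.12 are unaffected. The percentage in the text of 8.3.2.14 is a clerical slip that its own heading corrects.

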### **8.3.2.14 The 75% responder rate for Type IA1, IB, or IC seizure over the 12-week Maintenance Period**

50% responder rate in Type IA1, IB, or IC seizure over the 12-week Maintenance Period by each seizure type separately will be analyzed for the FAS, using the same logistic regression model as specified in Section 8.1.2.3.

### **8.3.2.15 Percent reduction in Type IA1, IB, or IC seizure frequency from Baseline, over the 12-week Maintenance Period and the 16-week Treatment Period**

The same methodology described in Section 8.2.2.3 will be applied. Analysis will be done by each seizure type separately.

### **8.3.2.16 Seizure-freedom status (yes/no) during the 12-week Maintenance and the 16-week Treatment Period**

Seizure freedom status will be evaluated for each treatment by summarizing the percentage of seizure-free subjects as a response rate during the 12-week Maintenance Period and during the entire 16-week Treatment Period. The seizure freedom rate will be calculated based on the Completer Set. The seizure freedom rate for each of these periods will be analyzed using an exact conditional logistic regression model where treatment group is included in the model and region and Baseline SV2A use are included as strata.

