The 16-week Treatment Period includes a 3-week Titration Period followed by a 1-week Stabilization Period and a 12-week Maintenance Period. Four weeks after the Screening Visit (Visit 1), subjects will return to the clinic for the Baseline Visit (Visit 2, Day 1). Subjects who continue to fulfill the inclusion and exclusion criteria will be randomized to 1 of the 5 treatment arms in a 1:1:1:1:1 ratio (random permuted blocks) to ensure the balance to 1 of the 5 treatment arms. Randomization will be stratified by current use of AEDs with binding to SV2A proteins (LEV or brivaracetam) and by region (North America, Europe, and Asia) at the time of randomization.

After the Baseline Visit (Visit 2), subjects will return to the clinic for regular visits for the remainder of the Titration Phase. Investigational medicinal product will be increased approximately every 3 to 7 days depending on treatment arms (refer to [Table 7-1](#) for details). Subjects will be instructed to take the IMP in 2 equally divided doses, approximately 12 hours apart in the morning and evening.

During the entire 16-week Treatment Period, the dose of concomitant AEDs and the settings for neurostimulation devices must remain stable. The dose of IMP should remain stable during the Maintenance Period.

Subjects who cannot tolerate IMP prior to Week 3 will be withdrawn from the study. For subjects with tolerability issues experienced at their target dose, one fallback option to a predefined dose based on the randomized dose (see [Table 7-2](#)) will be allowed during the Stabilization Period and at least 2 days prior to start of maintenance (Visit 4). The Study Physician or delegate should be consulted prior to use of the fallback option and the date as well as the reason for fallback will be recorded in the source documents and in the electronic Case Report form (eCRF).

Fallback may be managed via an unscheduled visit. Fallback IMP packs will be allocated via the Interactive Response Technology (IRT). After fallback, the dose will be kept stable for the rest of the Maintenance Period. Further dose changes (ie, titration) are not allowed. Subjects, who are not able to tolerate the IMP during titration and after the fallback, will be tapered off IMP in a blinded fashion and will be withdrawn from the study.

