13.3 Planned efficacy analyses

The efficacy variables will be analyzed as described below using the FAS.

Total seizure frequency per 28 days will be derived from the seizure count information recorded on the diary card and is defined as the number of seizures standardized to a 28-day period. It is computed as the number of seizures recorded over a period, divided by the total number of days in that period, multiplied by 28. Observable focal-onset seizures refers to Type IA1, IB, and IC seizures (according to the ILAE Classification of Epileptic Seizures, 1981). Focal-onset seizures include all Type I seizures. Seizure free status and seizure-free days include all (Type I, II, and III) seizure types.

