#### **3.5.4 Full Analysis Set**

The Full Analysis Set (FAS) consists of all subjects in the RS who were administered at least 1 dose or a partial dose of IMP and have Baseline and at least 1 post-Baseline seizure frequency data during the Treatment Period. In case of dosing administration error, or change in treatment dose, summaries and analyses will be conducted according to randomized treatment and not the actual treatment received. The FAS will be the primary analysis set for all efficacy summaries and analyses.

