### **3.5.6 Completer Set**

The Completer Set is a subset of the FAS, consisting of those subjects who completed the 16-week treatment period.

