#### **4.6 Use of an efficacy subset of subjects**

The FAS will be used as the primary analysis set for all efficacy analyses. Analyses using the PPS will also be performed for the FDA and European agency primary efficacy variables. The PPS analyses will provide additional information on efficacy evaluations and will describe findings in a subset of subjects who adhered more closely to the study protocol. No other efficacy subsets are defined for statistical analyses.

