#### **8.3.1.1 Seizure-freedom status (Yes/No)**

A subject is defined as seizure free (ie, seizure-freedom status=Yes) during a specific evaluation period if they meet all of the following criteria:

1. The subject completed the specific time period.
2. The subject did not have any missing diary days over the time period. Missing diary day refers to no diary available at all for that day. If the diary for the day is present and 'no seizures' is checked then the diary day is not missing.
3. The subject did not report any seizure of any type over the time period.

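### Seizure freedom is calculated and tested only in treatment completers, which removes dropouts from the denominator and raises the rate most in the arms that lose most subjects

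*SAP*

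**What the plan says.** SAP 8.3.2.16 covers seizure-freedom status over both periods. It fixes the denominator, "The seizure freedom rate will be calculated based on the Completer Set", and then the test: "The seizure freedom rate for each of these periods will be analyzed using an exact conditional logistic regression model", with treatment in the model and region and SV2A use as strata.

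SAP 3.5.6 defines the set: "The Completer Set is a subset of the FAS, consisting of those subjects who completed the 16-week treatment period".

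SAP 8.3.1.1 lists three conditions for a subject to count as seizure-free. The first is "The subject completed the specific time period"; the others are no missing diary days and no reported seizure of any type.

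Elsewhere the documents name a different population:

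- Protocol 13.3: "The efficacy variables will be analyzed as described below using the FAS". Protocol 13.3.3 adds that seizure freedom follows the same method as the other responder rates.
- SAP 3.5.4: "The FAS will be the primary analysis set for all efficacy summaries and analyses".
- SAP 4.6, after naming the FAS and the Per Protocol Set: "No other efficacy subsets are defined for statistical analyses".
- SAP 3.9 declares no change to any protocol-defined analysis.

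**The concern.** Completing 16 weeks is an outcome that arises after randomization and that treatment can influence. The protocol provides a route by which dose could do so: "Subjects who cannot tolerate IMP prior to Week 3 will be withdrawn from the study" (Protocol 5.1), and subjects who still do not tolerate treatment after the single fallback step are also withdrawn. A comparison among completers is therefore no longer the comparison that randomization protects.

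The restriction also solves no missing-data problem. Seizure-free status is already defined for every FAS subject, because anyone who did not complete is 'No'. The only effect of the Completer Set is to delete those 'No' results from the denominator. An arm that loses more subjects then shows a higher seizure-free rate because of its losses. Seizure freedom is a result that readers notice, and it would be reported with no FAS counterpart.

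**Working it through.** **Inputs from the documents**

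- 80 subjects per arm, 1:1:1:1:1 allocation (Protocol 13.8 and 5.1).
- A non-completer can never be seizure-free (SAP 8.3.1.1).
- Two-sided nominal 0.05, no multiplicity adjustment (SAP 8.3.2).
- The plan states no seizure-freedom rate and no dropout rate for this trial, so there is no planned figure to reproduce on this point. The only program figure is 11.9% discontinued at a data cut of the earlier open-label extension (Protocol 2.3.1).

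**Assumptions**

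- All 80 subjects per arm enter the FAS.
- Dropout ranges from 5% to 40%.
- S = 4 seizure-free subjects in each of two arms, so there is no true difference.

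**Step 1: inflation within an arm.** Let N be the FAS size, S the number seizure-free and d the proportion not completing. All S subjects are completers by definition.

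- FAS rate = S/N
- Completer Set rate = S/[N(1 − d)]
- Ratio of the two = 1/(1 − d)

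| Dropout d | 5% | 10% | 11.9% | 20% | 25% | 30% | 40% |
|---|---|---|---|---|---|---|---|
| 1/(1 − d) | 1.05 | 1.11 | 1.14 | 1.25 | 1.33 | 1.43 | 1.67 |

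**Step 2: distortion between arms.** With 4 of 80 seizure-free in each arm, the FAS gives 4/80 = 5.0% in both, odds ratio 1.00. On the Completer Set:

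| Dropout, placebo / padsevonil | Placebo rate | Padsevonil rate | Odds ratio |
|---|---|---|---|
| 10% / 10% | 4/72 = 5.6% | 4/72 = 5.6% | 1.00 |
| 10% / 20% | 4/72 = 5.6% | 4/64 = 6.3% | 1.13 |
| 10% / 30% | 4/72 = 5.6% | 4/56 = 7.1% | 1.31 |
| 5% / 40% | 4/76 = 5.3% | 4/48 = 8.3% | 1.64 |

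In the 10% / 30% case the rate ratio is (4/56)/(4/72) = 72/56 = 1.29 whatever the value of S. The odds ratio runs from 1.30 at S = 2 to 1.33 at S = 8.

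**Step 3: does another planned analysis cover this?** SAP 8.3.2.5 and 8.3.2.10 analyse the 100% responder rate in the FAS with the same exact model, but for observable focal-onset and Type I seizures rather than all seizure types. They also use the imputed frequencies of SAP 4.2.1.2. A subject who leaves during titration with at least 14 days of seizure data, none showing a seizure, has a frequency of zero carried forward and counts as a 100% responder. Non-responder imputation is planned only for the 75% responder rate (SAP 8.1.2.4.2). No FAS analysis of seizure-freedom status is planned.

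**The case against.** **The direction is not established.** No passage gives dropout by arm. Withdrawal criterion 6 (Protocol 6.3) removes subjects whose seizures worsen, and Protocol 5.4.1 asks investigators to consider withdrawing such subjects. If padsevonil works, those exits fall more on placebo and raise the placebo rate. The fallback dose is also meant to keep some intolerant subjects on treatment. This stands: the bias can go either way, and it favours padsevonil only where padsevonil loses more subjects.

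**Two effects must be kept apart.** The factor 1/(1 − d) raises the rate in every arm, placebo included. Only unequal dropout distorts the comparison; with equal dropout the odds ratio stays at 1.00. This also stands.

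**The effect is small and the endpoint minor.** In the 10% / 30% example the gap is 1.6 percentage points, and Fisher's exact test on 4/56 versus 4/72 gives p = 0.73; 4/48 versus 4/76 gives p = 0.71. At these counts a false positive is not the likely harm. The harm is a biased estimate. Seizure freedom is one of many other efficacy variables, tested at a nominal level, and no sample-size claim rests on it.

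**The SAP allows exceptions.** Section 8 makes the FAS the default unless noted otherwise, and 8.3.2.16 does note otherwise. SAP Amendment 3 added the Completer Set together with this analysis, so the sentence in 4.6 may simply be a leftover. That softens the conflict inside the SAP. It does not remove the departure from Protocol 13.3 and 13.3.3, which SAP 3.9 leaves undeclared, and it gives no reason for preferring completers.

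**Conclusion.** The concern holds. The current SAP text calculates and tests seizure freedom on a subset defined after randomization, although its own definition already classifies every dropout. Each arm's rate is inflated by exactly 1/(1 − d) relative to the FAS rate under that definition: 11% at 10% dropout, a third at 25%, 43% at 30%.

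The effect on the comparison depends entirely on how dropout differs between arms, which the documents do not give. Over the assumed range, equal seizure-free counts produce apparent odds ratios from 1.00 (equal dropout) to 1.64 (5% placebo, 40% padsevonil), with the sign reversed if placebo loses more. Neither primary analysis is affected. The change should be made, but the trial's main conclusions do not depend on it.

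**What to change.** In SAP 8.3.2.16, calculate and test seizure freedom in the FAS for both periods, counting subjects who did not complete the period as not seizure-free under the existing 8.3.1.1 definition. Keep the exact conditional model and strata as they are. Report the Completer Set rate as a descriptive supplement without a test, and mention that supplement in 4.6. Moving the analysis to the FAS restores the population named in the protocol. Any remaining difference from the protocol's method for seizure freedom, such as the exact conditional model, belongs in 3.9.

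The cost is one sentence in 8.3.2.16 and short consistency edits. No new data, model or sample size is needed. Reported seizure-free rates will be lower in every arm with dropouts.
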